Secondary Aims

2. Measure whether spinal cord perfusion can be improved during aortic cross clamp by improving collateral blood flow with regional anesthesia techniques.

Hypothesis: Near infrared spectroscopy (NIRS) values will decrease in the control and study group during aortic cross clamp but values in the study group will be 41% higher than control due to increased collateral blood flow.

Evaluation Method: Continuous measurement of spinal cord NIRS values during repair of aortic coarctation, including the aortic cross clamp period.

3. Determine the total time required for post-op ventilation in each group.

Hypothesis: Post-op ventilation times will be lower in those patients undergoing the experimental technique, paravertebral nerve block, because these patients will have less respiratory splinting from better analgesia and be less sedated from less sedative and analgesic use.

Evaluation Method: Time until extubation.

4. Determine the time to first feeding in each group.

Hypothesis: Patients who undergo the experimental technique, paravertebral nerve block, will have earlier return to feeding since they will have better analgesia and less sedation from narcotics.

Evaluation Method: Time until first feeding.

5. Measure stress response to surgery in the experimental and control groups.

Hypothesis: Patients who undergo the experimental technique, paravertebral nerve block, will have better suppression of the natural stress response to surgery.

Evaluation Method: Plasma epinephrine levels measured at baseline (before incision), postoperatively (just before transfer to the Intensive Care Unit), and 24 hours postoperatively.

Introduction, Background, and Significance to Our Mission

Repair of aortic coarctation is a commonly performed operation. The repair is performed via thoracotomy which is a surgical incision that is commonly complicated by atelectasis, desaturation, and pain in the adult population. To prevent these complications, it has been shown that regional or neuraxial anesthesia can decrease the amount of pain the patient has, which allows for deeper breathing and fewer desaturations from atelectasis. We propose, in this study, to examine the benefits of paravertebral peripheral nerve block in the neonatal and infant populations. Regional anesthesia has the potential to decrease narcotic requirements in children undergoing painful operations, decrease ventilator time, and manipulate the stress response to surgery. [1] [2] [3]

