Participants in the control arm will undergo an anesthetic consistent with the standard of care. The patient will be induced for anesthesia with propofol 3mg/kg or ketamine 2mg/kg (if there is intravenous access) or sevoflurane with 1 mcg/kg of fentanyl and 1.2 mg/kg rocuronium once IV access is established. The patient will be intubated; intravenous and intra-arterial access will be obtained and the patient will be positioned for surgery. A NIRS pad will be used for cerebral oximetry as well as another NIRS pad for spinal cord oximetry. Fentanyl may be used as needed for additional analgesia and anesthesia will be maintained with sevoflurane. The skin will be infiltrated at the conclusion of surgery with less than 1 mL/kg of 0.25% bupivacaine with epinephrine 1:200k. The patient will be returned to the ICU intubated unless the anesthesia provider considers them to be an excellent candidate for early extubation. Every patient will have an epinephrine level drawn pre-incision in the operating room, post-operatively upon arrival to the intensive care unit, and 24-hours post-operatively (unless there is no existing vascular access that allows the level to be drawn 24-hours post-operatively). The 24-hour post-operative time point will be defined as 24-hours after arrival to the CICU.

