Participants in the experimental arm will undergo an anesthetic that includes the regional anesthetic technique, paravertebral nerve block. The patient will be induced for anesthesia with propofol 3mg/kg or ketamine 2mg/kg (if there is intravenous access) or sevoflurane with 1 mcg/kg of fentanyl and 1.2 mg/kg rocuronium once IV access is established. A NIRS pad will be used for cerebral oximetry as well as another NIRS pad for spinal cord oximetry. The patient will be intubated, and then will be positioned laterally for the nerve block at approximately the left T3-4 level. A 13-6 MHz, linear ultrasound probe with a sterile sheath will be used to provide imaging for the paravertebral nerve block. A Pajunk SonoPlex 50mm, 22 gauge, facet tip needle will be used. The injected solution will be 1 mL/kg of 0.2% ropivacaine with 5 mcg/mL (1:200k) epinephrine. Ropivacaine is a standard drug used in this patient population for regional nerve blocks and is non-experimental as part of this protocol. The paravertebral block needle insertion site and sterile field will be observed and the block will be performed or supervised by one of the study investigators. Fentanyl may be used as needed for additional analgesia and anesthesia will be maintained with sevoflurane. The skin will not be infiltrated with additional local anesthetic at the conclusion of the case. Every patient will have an epinephrine level drawn pre-incision in the operating room, post-operatively upon arrival to the intensive care unit, and 24-hours post-operatively (unless there is no existing vascular access that allows the level to be drawn 24-hours post-operatively). The 24-hour post-operative time point will be defined as 24-hours after arrival to the CICU.

Post-operative pain control in either the control or experimental (paravertebral nerve block) group will be accomplished with intravenous, rectal, and oral analgesics. Patients will receive scheduled rectal acetaminophen while intubated and oral acetaminophen once they have progressed to oral intake of formula. Intravenous fentanyl or morphine will be used for

breakthrough pain while intubated and until oral intake is tolerated. Once oral intake is resumed, the patient will be provided with oral oxycodone as needed for pain and additional doses of IV morphine as needed for severe pain.. If the patient is not yet ready for extubation and requires additional sedation, intravenous doses of midazolam may be required.

Sample Size/Statistics

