Descriptive statistics will be calculated for all variables of interest and include means and standard deviations, medians and ranges or counts and percentages, as appropriate. Summary measures will be tabulated overall and by treatment group. Recruitment and consent rates will be calculated with associated 95% confidence intervals. Primary and secondary outcomes will be compared between the two intervention groups. Continuous measures will be compared between groups using two-sample t-tests or Wilcoxon rank-sum tests while categorical variables will be compared using Chi-square tests or Fisher exact tests. Because this is a pilot study, effect sizes will be calculated for all outcomes and will include difference in means, difference in rates, or risk ratios with associated 95% confidence intervals. Analysis will follow the intention to treat principal where all subjects are analyzed based on their randomly assigned treatment whether or not they received the treatment. A p-value less than 0.05 will be considered statistically significant and all statistical testing will be two-sided, unless otherwise noted. Analysis will be conducted using SAS v. 9.4 (Cary, NC) and under direction of the pediatric biostatistics core.

Adverse Event Reporting

Monitoring of Adverse Events (AEs) and Serious Adverse Events (SAEs) is an important aspect of data collection. The study subjects will be reviewed on a case-by-case basis. The principal investigator will determine the seriousness of each adverse event and whether or not the event

was related to the study. Adverse events potentially associated with paravertebral nerve blocks include (from most to least common): block failure, vascular puncture, deep tissue hematoma (SAE), epidural hematoma (SAE), hypotension, lung puncture, pneumothorax, and local anesthetic systemic toxicity (SAE). Hypotension will be defined as a mean arterial pressure less than 30 mm Hg during the first 24 hours after arrival to the CICU.

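### Clamp-period spinal NIRS is compared between arms without baseline adjustment; the test is valid, but it gives up precision if pre-block and clamp-period readings correlate above about 0.2

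*Combined protocol and SAP*

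**What the plan says.** Under Sample Size/Statistics, primary and secondary outcomes are compared between arms, and "Continuous measures will be compared between groups using two-sample t-tests or Wilcoxon rank-sum tests". No covariate, analysis of covariance or change score appears anywhere. The same paragraph adds: "Because this is a pilot study, effect sizes will be calculated for all outcomes", with 95% confidence intervals.

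Spinal NIRS is the outcome of Aim 2 under Secondary Aims. Its evaluation method is "Continuous measurement of spinal cord NIRS values during repair of aortic coarctation, including the aortic cross clamp period". Its hypothesis is about levels during the clamp: "values in the study group will be 41% higher than control due to increased collateral blood flow". No baseline window is given, and no single clamp-period value per infant is named.

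Under Study Description, both arms have the sentence "A NIRS pad will be used for cerebral oximetry as well as another NIRS pad for spinal cord oximetry". In the experimental arm it comes before intubation, lateral positioning and the block. In the control arm it comes after intubation, line placement and positioning for surgery. Neither paragraph says when recording starts.

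**The concern.** Infants are likely to differ in spinal NIRS before any treatment effect can arise. If those differences persist into the clamp period, an unadjusted comparison leaves them in the error term. A baseline covariate would remove part of them, and the monitor that would supply it is already in use. At 15 per arm the confidence interval is wide, so a cheap gain in precision is worth having.

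Two gaps stand in the way. A two-sample test needs one number per infant, and a continuous trace does not supply one until a summary is chosen. A covariate needs a reading taken before treatment in both arms. The documents make this plausible but do not guarantee it, and a reading taken after the block would be post-treatment in the experimental arm.

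What is at stake is the width of one secondary interval. The future sample size rests mainly on morphine equivalents, which this point does not touch.

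**Working it through.** **Inputs from the documents.** 15 per arm, N = 30, 1:1 randomised; two-sided 0.05; two-sample t-test or Wilcoxon test; hypothesised NIRS difference 41%. The plan gives no power figure for NIRS, so there is none to reproduce. Its statement that 15 per arm is adequate concerns a 36% fall in morphine consumption and comes without an SD.

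**Assumed.** The baseline-to-clamp correlation r, the NIRS SD, the number of missing baselines, and normal data unless stated.

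**Step 1: break-even.** With one normal covariate and 1:1 allocation, the expected variance of the adjusted difference relative to the unadjusted one is

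(1 − r²) × (N − 3)/(N − 4).

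At N = 30 and r = 0 this is 27/26 = 1.038. Setting it to 1 gives r² = 1/(N − 3), so r = √(1/27) = 0.192. On CI width, with t on 27 rather than 28 degrees of freedom, break-even is 0.201. With fewer infants the variance break-even rises to √(1/21) = 0.218 at N = 24 and √(1/17) = 0.243 at N = 20. These values are for the t-test and do not carry over exactly to the Wilcoxon option.

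**Step 2: interval width at 15 per arm.** With the SD at its true value, the unadjusted half-width is 2.048 × √(2/15) = 0.748 SD. Averaged over samples it is 0.74 SD, because the sample SD runs slightly low. The last three columns come from simulation.

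| r | Variance factor | CI width, adjusted/unadjusted | Mean half-width, adjusted | Adjusted interval narrower in |
|---|---|---|---|---|
| 0 | 1.038 | 1.02 | 0.76 SD | 20% of trials |
| 0.3 | 0.945 | 0.97 | 0.72 SD | 60% |
| 0.5 | 0.779 | 0.88 | 0.65 SD | 91% |
| 0.7 | 0.530 | 0.73 | 0.54 SD | over 99% |

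Type I error was close to 5% for both methods at every r. With 10 usable infants per arm the width ratios are 1.03, 0.99, 0.90 and 0.74. With bounded readings (assumed baseline ceiling at +0.5 SD and clamp floor at −1 SD) the gain shrinks: 0.98, 0.92 and 0.81 at r = 0.3, 0.5 and 0.7.

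**Step 3: missing baselines.** Ordinary regression drops an infant with no baseline. The simulation assumes equal losses in the two arms, unrelated to the readings. The unadjusted half-width with all 30 infants is 0.74 SD.

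| r | Baselines lost per arm | Infants dropped | Missing baseline set to overall mean |
|---|---|---|---|
| 0.3 | 1 | 0.75 SD | 0.72 SD |
| 0.5 | 3 | 0.74 SD | 0.68 SD |

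Dropping infants removes the gain in both cases. Filling in the mean keeps all 30 and restores most of it, with type I error near 5%.

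**Step 4: against the 41% hypothesis.** Write the SD as a share of the control mean (assumed). The standardised difference is 0.41/SD, and power comes from the noncentral t at 15 per arm.

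| SD | Standardised difference | Power, unadjusted | Power, adjusted at r = 0.5 |
|---|---|---|---|
| 20% | 2.05 | over 99% | over 99% |
| 30% | 1.37 | 95% | 98% |
| 40% | 1.02 | 77% | 87% |
| 50% | 0.82 | 58% | 69% |

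At an SD of 30% the half-width goes from 0.74 × 30 = 22% of the control mean to 0.65 × 30 = about 20% at r = 0.5.

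**The case against.** The planned analysis is not an error. Unadjusted differences with 95% intervals are a legitimate plan for a pilot that describes itself as probably underpowered. The benefit of adjustment rests on a correlation that nobody has stated: below about 0.2 it is a small loss, and up to about 0.3 a small gain. Aim 2 attributes the clamp-period difference to collateral flow, and nothing there implies that a pre-block reading predicts it. The power gains also need an SD of 40–50% of the control mean. All of this stands. It makes the point a low-priority improvement, but it does not remove it, because the worst-case cost is about 2% of interval width.

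It also stands that adjustment applied carelessly can do harm. No pre-block reading is guaranteed, and dropping infants without one can cancel the gain, so a missing-baseline rule has to be part of the change.

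A reader might infer that chance imbalance in baseline NIRS biases the planned comparison. It does not: randomisation makes the comparison unbiased, and its interval already allows for such imbalance. A reader might also infer from the order of description that recording starts at different times in the two arms. The text does not fix the timing either way; it only leaves it open.

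A third tempting reading is that the epinephrine comparison is biased because the pre-incision sample may follow the block, whose solution contains epinephrine ("The injected solution will be 1 mL/kg of 0.2% ropivacaine with 5 mcg/mL (1:200k) epinephrine"). The plan's comparison of post-operative levels never uses that sample, so the argument would count only against adjusting for it.

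**Conclusion.** The point holds as one of precision. The unadjusted NIRS comparison is valid. It is less precise than a baseline-adjusted one if r exceeds about 0.2 with 30 analysable infants (about 0.24 with 20). The gain is slight at r = 0.3, about 12% of interval width at r = 0.5 and 27% at r = 0.7. It is smaller if readings hit a floor or ceiling or if baselines are missing. These sizes rest on assumed correlations and simulated normal data.

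The documents do not support saying that the NIRS result would be wrong, that the study cannot detect the hypothesised difference, or that the morphine estimate is affected. The unnamed clamp-period summary is missing detail rather than a faulty method. It still needs settling in advance, because the trial is unblinded and a mean, a nadir or an end-of-clamp value could otherwise be chosen after the data are seen. The point is worth considering, with medium confidence.

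**What to change.** For spinal NIRS:

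1. State that recording starts before the block in the experimental arm, and at a matching point after intubation and before incision in the control arm. Use that window as baseline in both.
2. Name one clamp-period summary per infant before the data are seen. The time-weighted mean is one choice; another could be justified.
3. Compare arms by linear regression on arm plus baseline and report the adjusted difference with its 95% CI. Keep the planned t-test or Wilcoxon test as a sensitivity analysis.
4. Keep every infant with a clamp-period value in the model, replacing a missing baseline with the overall baseline mean across both arms.

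The cost is SAP wording, a protocol clarification on recording start, one degree of freedom, and an interval about 2% wider if r is 0 (about 3% with 10 per arm).

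Epinephrine is a separate matter. Keep the planned comparison. Reconcile the time of the post-operative sample, which Aim 5 places shortly before the infant leaves for intensive care and Study Description places on arrival there.

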Pain remains a significant concern in the neonatal and infant populations. There is evidence that pain is often undertreated in order to accomplish other goals of medical management including earlier extubation. Furthermore, pain control with narcotic medications are an additional concern and withdrawal from narcotics can become an issue in those neonates and infants requiring long-term administration of these medications. Therefore, further study into alternative methods of pain control are warranted.

Significance:

Specific Aim #1:

Use of paravertebral nerve block in these patients may improve pain control for these patients and decrease the total burden of narcotic administered.

Specific Aim #2:

Use of regional anesthesia to encourage collateral blood flow may be spinal cord protective as evidenced by an improvement in the NIRS during aortic cross clamp in the experimental group.

Specific Aim #3:

Decreased time to extubation may be made possible in the experimental group, which would help to prevent ventilator associated complications including barotrauma, pneumothorax, pneumomediastinum and ventilator associated pneumonia.

Specific Aim #4:

Decreased time to first feeding may be facilitated by earlier extubation and less sedation in the experimental group.

Specific Aim #5:

Decreased stress response to surgery is generally associated with fewer physiologic perturbations and may be facilitated by the use of regional anesthesia compared to the standard of care group.

Experimental Design and Methods

Design:

This study is designed to be a prospective, randomized, non-blinded clinical trial. After informed and written parental consent, a total of 30 neonates and infants (<1 year old) will be enrolled. Subjects will be assigned to nerve block or SOC in a 1:1 ratio. Random treatment assignment

will be accomplished using a permuted block design with random block sizes of 2 or 4. Randomization will be done by study statistician using SAS v. 9.4 (Cary, NC).

Study Population:

A total of 30 neonates and infants, defined as children less than 12 months of age, will be enrolled in this study. The subjects will be scheduled for elective or semi-elective cardiac surgery at Children's Healthcare of Atlanta.

The following criteria will be used to determine patient eligibility:

Inclusion Criteria:

- Neonate or Infant (<12 months age) at the time of surgery
- ≥ 2.5 kg at the time of surgery
- Undergoing aortic coarctation repair via left thoracotomy

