This protocol is designed as a pilot study with limited-efficacy testing. The primary goal is to demonstrate the feasibility of a subsequent randomized clinical trial. In doing so, we will assess the capacity for recruitment and caregiver consent to random assignment. An additional exploratory aim is to evaluate the preliminary efficacy of using a single-shot paravertebral nerve block to decrease perioperative morphine consumption. Because this is a pilot study, the proposed study is likely underpowered to detect a statistically significant result. However, the results (i.e. effect sizes) from this study will be used in sample size and power calculations for a future, larger RCT. We expect that there will be a trend toward lower morphine equivalent consumption in the experimental group that will either reach statistical significance or provide a better estimation of necessary sample size for future funding from extramural sources.

The most similar study available for comparison examined the use of paravertebral nerve catheters in infants undergoing thoracotomy to repair long-gap esophageal atresia. This study was retrospective and several days of morphine consumption were observed. In this retrospective trial of 17 patients, the authors observed a decrease of 36% in morphine consumption per day ($p<0.001$).[6] If such a dramatic decrease in morphine consumption is observed during our prospective study, then it is adequately powered at current sample size 15 in each arm, total 30 patients.

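### All infants under 12 months are pooled, unstratified and 15 per arm, and compared without adjustment; pre-specifying one baseline covariate (weight or age) would be a cheap, though not free, improvement

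*Combined protocol and SAP*

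**What the plan says.** Eligibility (Inclusion Criteria) is broad in age, "Neonate or Infant (<12 months age) at the time of surgery", and has a lower weight limit only, "≥ 2.5 kg at the time of surgery". Under Design, "a total of 30 neonates and infants (<1 year old) will be enrolled" and "Subjects will be assigned to nerve block or SOC in a 1:1 ratio", by a "permuted block design with random block sizes of 2 or 4". No stratification factor is named.

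For the analysis, the Sample Size/Statistics section states: "Continuous measures will be compared between groups using two-sample t-tests or Wilcoxon rank-sum tests". Categorical outcomes get chi-square or Fisher tests. Effect sizes are differences or risk ratios with 95% confidence intervals. No covariate appears in any planned comparison.

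Two other statements bear on this. The Primary Aim's evaluation method adds up narcotics over 48 hours and converts them to morphine equivalents, with no division by body weight stated. The Sample Size/Statistics section says that the effect sizes will feed the sample size and power calculations of a larger trial.

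**The concern.** Newborns and infants close to their first birthday can differ in size, in opioid given, and possibly in ventilation time, feeding time, epinephrine and NIRS values. With 15 per arm, chance alone can put noticeably more small or young infants in one arm. Nothing in the design or analysis allows for that, although age and weight must be known for every infant to establish eligibility.

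At stake are the width of the intervals and the reliability of the single estimate carried into planning the next trial. The opioid total is the most exposed outcome: if doses are given roughly by weight (assumption; the documents state this for induction fentanyl but give no postoperative opioid doses), an unscaled total rises with weight by construction. If imbalance is noticed only after the data are in, any adjustment chosen then is post hoc.

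**Working it through.** **Inputs from the documents.** N = 30, 15 per arm, two-sided 5% level, unadjusted tests, a 36% reference effect. **Assumptions, because the documents are silent.** The share of neonates, the correlation of age or weight with each outcome, and the coefficients of variation (CV).

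**1. The plan's own figure.** The reference is a retrospective study in which "the authors observed a decrease of 36% in morphine consumption per day"; if that is seen here, "then it is adequately powered at current sample size 15 in each arm, total 30 patients". No mean, SD or target power is given, so this cannot be reproduced. With 15 per arm and a t-test on 28 df, 80% power needs a standardised difference of 1.06, so a 36% drop suffices only if the CV is at most 0.36/1.06 = 0.34. At a CV of 0.5, power is 48%. Precision is therefore scarce unless variability is low.

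**2. How often the arms differ.** Suppose 15 of the 30 are neonates (assumption). The number in one arm is then hypergeometric (30, 15, 15), with C(30,15) = 155,117,520.
- Difference of 1: 2 × 6,435² / 155,117,520 = 0.534
- Difference of 3: 2 × 5,005² / 155,117,520 = 0.323
- Difference of 3 or more: 1 − 0.534 = 0.466
- Difference of 5 or more: 0.466 − 0.323 = 0.143

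For a continuous covariate, the standardised difference between arms has SD √(2/15) = 0.365. It exceeds 0.5 SD in 17% of randomisations.

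**3. What such a difference does.** A 9 v 6 split is (3/15)/0.5 = 0.4 SD of the neonate indicator. At a correlation of 0.4–0.6 it moves the outcome difference by 0.16–0.24 SD. The unadjusted 95% half-width is 2.048 × 0.365 = 0.75 SD.

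**4. Cost and gain of adjustment.** With k covariates, the expected CI width relative to the unadjusted one is approximately √[(1 − R²)(N − 3)/(N − k − 3)] × t(28 − k df)/t(28 df).
- One covariate, cost factor: √(27/26) × 2.052/2.048 = 1.021; break-even R² = 1 − 1/1.021² ≈ 4%
- Two covariates, cost factor: √(27/25) × 2.056/2.048 = 1.043; break-even R² = 1 − 1/1.043² ≈ 8%

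| Correlation (R²) | One covariate | Two covariates (joint R²) |
|---|---|---|
| 0 (0) | 1.021, 2% wider | 1.043, 4% wider |
| 0.4 (0.16) | 0.917 × 1.021 = 0.936, 6% narrower | 0.917 × 1.043 = 0.956, 4% narrower |
| 0.6 (0.36) | 0.80 × 1.021 = 0.817, 18% narrower | 0.80 × 1.043 = 0.834, 17% narrower |

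**5. Is break-even likely for the opioid total?** If total = weight × per-kg use, with the two independent (assumption), weight's R² is a²/(a² + b² + a²b²), where a is the CV of weight and b that of per-kg use.
- a = 0.35: 10% (b = 1.0) to 30% (b = 0.5)
- a = 0.25: 6% (b = 1.0) to 19% (b = 0.5)

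All exceed the one-covariate break-even of 4%. The 6% corner falls below the two-covariate break-even of 8%.

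**6. Validity and power by simulation.** 20,000 trials per setting, with normal covariates, an age–weight correlation of 0.8 and both covariates in the model (all assumptions).
- Unadjusted type I error over all trials: 4.6–5.1%, with mean bias about zero.
- Unadjusted type I error among trials with an age–weight imbalance above 0.5 SD: 4.7% at R² = 0, 7.5% at 0.1, 12.2% at 0.3 and 19.0% at 0.5. Adjusted, it stays at about 4.5–5.2%.
- Starting from about 80% unadjusted power, adjusted power is 76.5% at R² = 0, 80.9% at 0.1, 85.7% at 0.2 and 90.0% at 0.3.

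**The case against.** The strongest defence is that nothing here is invalid. Randomisation protects the unadjusted test, and its interval already carries chance imbalance; the 9 v 6 split above shifts the estimate by well under the half-width. Feasibility is the primary goal, efficacy is exploratory, and the plan itself expects to be short of power. Unadjusted estimates with intervals are a legitimate pilot analysis, and an adjusted residual SD helps the next trial only if that trial adjusts in the same way. All of this stands, and it makes the point an improvement rather than the correction of an error. It does not remove the conditional problem: the next trial inherits one realised estimate, not the average over randomisations.

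A reader might infer three stronger things that the documents do not support.
- **That chance imbalance enters every comparison.** It matters only for outcomes related to age or weight. Recruitment and consent rates are not arm comparisons and are untouched.
- **That adjusting for both age and weight is free.** No new data are needed, but at N = 30 two covariates lose precision below a joint R² of about 8%. Age and weight are probably collinear in this age range (assumption), so the second may add little.
- **That per-kg scaling already settles the opioid outcome.** No such scaling is stated.

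A single log-linear model for everything would also fail. The control-arm paragraph of the Study Description lets an infant be extubated before return to the ICU, so postoperative ventilation time can be zero.

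**Conclusion.** The point holds as a low-cost improvement. The plan pools a wide age and weight range with 15 per arm, does not stratify, and specifies no adjusted analysis. The unadjusted tests are valid on average. What is lost is precision, and protection of the realised estimate against imbalance on a prognostic covariate. For one covariate the worst case is a CI about 2% wider, against one about 6–18% narrower at a correlation of 0.4–0.6. For both covariates the corresponding figures are about 4% wider and about 4–17% narrower.

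The size of the gain rests on correlations that the documents do not give. The 47% and 14% imbalance figures rest on half the infants being neonates. The case is firmest for the opioid total, where weight is likely to be prognostic if dosing follows weight.

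**What to change.** Add to the Sample Size/Statistics section:
- For the 48-hour morphine-equivalent total, a linear model with arm and weight at surgery, reporting the adjusted difference and 95% CI beside the planned unadjusted test.
- For each other continuous outcome where a linear model is suitable, the same with arm and one covariate, age or weight, named in advance for each outcome.
- Where values can be zero or are heavily skewed, such as ventilation time, a rank-based or other suitable adjusted method, also named in advance.

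Keep the unadjusted estimates, so that the next trial can be sized with or without adjustment. Stratifying the randomisation is not needed for this. The cost is a few lines of text, one extra analysis per outcome, one degree of freedom in each linear model, and no new data.
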